14 INFORMED CONSENT

14.1 Consent Procedure

Informed consent will be sought and will be collected by a member of the site research team listed on the delegation log from each participant before they undergo any study-related procedures or interventions related to the study. A member of the site research team will explain the details of the study, direct the participant to the explainer animation, in addition to the already presented Participant Information Sheet (PIS), ensuring that the potential participant has sufficient time to consider participating or not. A member of the site research team (authorised to do so on the delegation log) will answer any questions that the potential participant has concerning study participation.

The study will be open to patients from 14 years of age if they meet the inclusion criteria. Specific participant information and consent forms has been designed for young people. All consent and participant information has been carefully designed with the support of our PPI panel and team members, to ensure that those invited to take part will be well informed prior to providing consent.

For adolescents aged under 16 years, their parent/guardian will be provided with the Parent/Guardian PIS and asked to sign the Parent/Guardian Consent Form (on behalf of adolescents aged 14-15 years), and the adolescent will be provided with the 14-15 years PIS, and an assent form to sign. If any adolescent indicates dissent or indicates they do not want to take part, they will not be included in the study.

For adolescents aged 16 years and over and deemed to be competent to give consent to participate (based upon their capacity to understand the specific circumstances and details of the research being proposed), they will be provided with the adult PIS and asked to sign the adult Consent Form and give their own consent to participate.

Adolescents that consented when aged 14-15 years but reach 16 years during the study, will be contacted (via their Parent/Guardian) by sites and asked to consent to continue their participation by signing the Continuing Consent Form (for ages 16 years). Remote eConsent and paper options will be available. If the participant does not want to continue in the study, they will be withdrawn from the study following the process outlined in Section 17.6.

14.2 Time allowed to decide to take part

It is important that potential participants are under no pressure to decide whether they want to take part, so no time limit is applied, however, investigators should be mindful of the expedited nature of the pathway of this study.

14.3 Completion of the Informed Consent Form

The potential participant or parent/guardian (where applicable) and the Investigator (or authorised designee) must personally sign and date the current approved version of the informed consent form.

The Informed Consent Form will usually be offered to participants in clinic as an electronic form on a tablet device (with the consent form being filled in directly on REDCap), however, paper consent forms will also be made available for use in situations where electronic consent is not possible or suitable. Where it is not possible for a consent form to be completed in clinic (for example, if a participant has only had telephone appointments), remote electronic consent may also be used.

Where consent forms are completed electronically signatures will be either achieved by a finger tracing across a tablet device, using an electronic stylus on a tablet device or using a mouse dragging the cursor across the screen – all methods are to be used as if signing with a traditional pen.

A copy of the fully signed consent form will be given to the participant, and the central CTU study team (if the participant has agreed to either of the optional aspects of consent - see Section $\underline{14.4}$).

Where electronic consent (using REDCap) is used in clinic and the participant or parent/guardian has an email address, they are willing to provide, an electronic version of the signed ICF will be automatically emailed to them. If the participant does not have/does not provide an email address the site research team will be able to print a copy of the signed ICF and provide this to the participant. A downloaded copy of the electronic consent should be placed in the Investigator Site File and a copy in the participant's medical record.

Remote eConsent (using REDCap) will be obtained in accordance with OCTRU's standard operating procedure for obtaining consent. Where remote consent will be used, potential participants will be asked to provide an email address for receiving consent documents prior to obtaining written informed consent. Potential participants will receive a unique link via email to an electronic consent form which may then be completed remotely. Once completed this form will be countersigned by a member of the site research team authorised to do so and then sent, via email, to the participant as a PDF document. A member of the site research team will be required to countersign all consent forms completed remotely, in the same way as for paper forms, and verify the identity of the participant. Patients who do consent to study participation will receive a copy of the fully completed consent form via email once this has been countersigned.

For those that receive a link but decide not to take part, their email address will be deleted from the data collection system no later than four weeks after the form has been emailed.

14.4 Optional aspects of consent

The participant/parent/guardian may agree to be contacted (upto the time their child turns 16 for parents/guardians) about ethically approved research studies for which they may be suitable (for up to five years from the point after the study has finished). By agreeing to be contacted this would not oblige them to participate in any further studies. The participant may also agree to the retention of their NHS/CHI number for up to five years from entry into the study to enable long term follow up using routinely collected NHS national data.

Both are optional aspects of the consent process. Participation in these elements of the research is voluntary and refusal to participate will not affect their inclusion in the clinical study. Refusal to participate will involve no penalty or loss of benefits to which the individuals would otherwise be entitled or their standard management in any way.

14.5 Individuals lacking capacity to consent

Individuals lacking capacity to consent to study participation will not be eligible to enter the study.

14.6 Participants who lose capacity during the study

Participants who consent and are included in the study who lose capacity during the study will be withdrawn and have their data available for use up until the point when they lose capacity. After this point ongoing consent is not valid.

14.7 GP notification

Permission from the participant will also be obtained to inform their GP of their inclusion in the study. An approved GP letter will be sent by the ACL STARR central CTU study team together with study information to the participant's GP surgery informing them of their participation in the study for those that go on to be randomised.

14.8 Re-consenting

Should there be any subsequent amendment to the final protocol, that might affect a participant's participation in the study, continuing consent will be obtained using an amended consent form which will be signed by the participant.

Continuing consent will also be sought from those participants who reach their 16th birthday during the intervention period or during follow up, who were originally consented into the trial by their parent or guardian.

15 RANDOMISATION

15.1 Timing of randomisation

Randomisation will only be performed when informed consent has been obtained, once baseline questionnaires have been completed and final eligibility confirmed in theatre.

15.2 Randomisation procedure

Initial eligibility / final eligibility will be confirmed at the point of randomisation. Participants will be randomised by the site research team using REDCap.

Participants will be randomised to one of the following arms:

Arm	Treatment (or Description)		
Arm 1 ACL Repair (intervention)	This group will have surgery to repair the ACL, with the		
	ligament being stitched back onto the bone.		
Arm 2 ACL Reconstruction (usual	This group will have surgery to reconstruct the ACL. This will		
care/comparator/control arm)	involve replacing the torn ACL with other tissue i.e.		
	hamstring to act as a replacement.		

Upon randomisation of a participant, the ACL STARR central CTU study team and a member of the site research team will be notified by an automated email. Full details of the randomisation procedure will be stored in the Randomisation and Blinding Plan in the confidential statistical section of the TMF.

15.3 Randomisation methodology

Participants will be randomly allocated to one of two treatment options (1:1) via automated, secure (encrypted), web-based randomisation provided by the Oxford Clinical Trials Research Unit (OCTRU) using a REDCap platform.

Random allocation will be implemented using a minimisation algorithm with stratification factors: preinjury Tegner score (2 groups (0-6, 7-10)), planned lateral extra-articular procedure (yes, no) and site. The minimisation algorithm will be seeded with several allocations and a non-deterministic probabilistic element will be introduced to prevent predictability of the treatment allocation.

Patients not randomised in theatre will be managed along the normal standard of care pathway.

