11.5 Rationale for inclusion and exclusion criteria

A paediatric population has been included within the study at the request of paediatric knee community and BSCOS, and their recommendations for an RCT in ACL repair⁽¹³⁾. Our lower age limit within this study is 14 years. Adolescent ACL injuries have a high associated re-rupture rate^(33, 34) in comparison to the adult age group and evidence exists suggesting repair is an option for avulsion type ACL injuries. This cohort therefore has a high potential benefit from the results of the study. ACL injuries have a low frequency below the age of 14 years (as the bone typically fractures instead when younger). They will be managed within specialist centres who regularly manage adolescent patients.

^{*}A proximal tear will be diagnosed on review of the MRI scan, and eligibility will be confirmed intra-operatively on arthrospopic inspection, to confirm a Sherman Type 1 or Type 2 tear and acceptable tissue quality for repair (i.e. an intact synovial sheath surrounding the torn ACL as a single unit).

It is at age 14 years upwards that paediatric knee surgeons would be in equipoise and happy to randomise for repair or reconstruction.

Upper age limit: We have not set an upper age limit to help ensure the study is inclusive and research findings will be applicable to the population. This will be left to a pragmatic decision of the treating surgeon based on clinical presentation.

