23.2 Sample Size/Power Calculations

The sample size calculation was premised upon a 1:1 randomised parallel group trial design with an analysis of the primary outcome (KOOS-4) using mixed-effects linear model adjusted for randomisation variables and baseline KOOS-4. Standard nominal 2-sided 5% significance level was adopted, and the power for detecting a between group difference of 8 and 9 points in the KOOS-4, was assessed for a missing data allowance of 15%.

We considered a variety of scenarios varying the adjustment for baseline correlation and desired statistical power. (See Table 4 below for a selection)

Table 4 – Sample size scenarios; all based upon 2-sided 5% significance level, 1:1 allocation continuous outcome, pooled SD of 20, and non-central-t distribution calculation [Stata power two means command]

No.	Target difference	Statistical Power	Missing data allowance	Adjusted for baseline	Sample size required (overall)
1	8	80	15%	No	236
2	8	90	15%	No	314
3	9	80	15%	No	186
4	9	90	15%	No	248
5	8	80	15%	Yes	204
6	8	90	15%	Yes	272
7	9	80	15%	Yes	162
8	9	90	15%	Yes	214

An overall sample size of 236 and 186 is required for 80% power for a difference of 8 points and 9 points respectively given a pooled standard deviation (SD) of 20 points. Equivalent 90% power, required number of observations are 314 and 248 respectively.

However, the expected sample size required is lower given the planned adjustment for baseline KOOS-

4 score as the effective variability is reduced. Implementing this using the formula provided by Borm⁽³⁹⁾ using a correlation between baseline and follow-up score of 0.37 leads to requiring only 204 and 272 for 80% and 90% power for a target difference of 8 points or equivalently 162 and 214 (all other assumptions and inputs as before) for 9 points difference. Therefore, we have opted for a sample size of 214 (no. 8, table 2) randomised participants which allows for 15% missing data for a target difference of 9 points (at 90% power). This sample size also ensures more than 80% power for a target difference of 8 points (no. 5, Table 2).

We anticipate that 25% of those who consent to be assessed as unsuitable for repair intra-operatively, we expect approximately 286 will need to be consented. The intraoperative assessment at arthroscopy has been shown to be crucial to determine the repairability of the ligament and reduce failure rate $^{(40)}$.

Justification of sample size inputs

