23.3.1 Primary outcome

The primary outcome (KOOS-4 at 24 months) will be compared using a mixed-effects linear model to calculate the mean difference between treatment groups. Treatment, baseline KOOS-4 and planned lateral extra-articular procedure will be incorporated as fixed effects and recruiting site as a random effect. Results will be presented as estimates and 95% CIs whenever possible. A sensitivity analysis will be conducted that removes participants aged 20 years or younger at the time of completing baseline KOOS-4. Sensitivity to missing data will also be explored using informative missing to confirm tolerance to differential mechanisms (using a pattern-mixture model approach).

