23.5 Subgroup analysis

Secondary subgroup analyses of the primary outcome will investigate visually, presenting using forest plots, whether treatment effects vary by the key clinical factors (baseline KOOS-4 level, and planned lateral extra-articular procedure, and age group (<20 years, 20 years and over).

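### Age is in neither the minimisation nor the primary KOOS-4 model, although eligibility starts at 14 with no upper limit; prespecifying it as a covariate would be a near-costless improvement

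*Protocol*

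**What the plan says.** **Who is eligible.** Section 11.3 sets the lower age limit at 14, and section 11.5 states that there is no upper limit.

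**How the protocol regards age.** Section 11.5 says "Adolescent ACL injuries have a high associated re-rupture rate" when compared with adults. Section 8 refers to high failure rates after reconstruction in children and adolescents. Section 13 puts age first among the risk factors behind the surgeon's decision on a lateral extra-articular procedure (LEP). Section 23.5 includes "age group (<20 years, 20 years and over") among the factors for subgroup analysis of the primary outcome.

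**What is balanced.** Section 15.3 minimises on pre-injury Tegner group (0-6, 7-10), "planned lateral extra-articular procedure (yes, no) and site". Section 15.3.1 justifies each of these, conceding that it is unknown whether planned LEP is a confounder. It does not discuss age.

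**What is adjusted for.** Section 23.3.1 states: "Treatment, baseline KOOS-4 and planned lateral extra-articular procedure will be incorporated as fixed effects and recruiting site as a random effect". The same section adds a sensitivity analysis that drops everyone aged 20 or younger.

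**The concern.** The protocol widened the age range on purpose and describes the young as a higher-risk group for re-rupture. It then controls for a factor whose relevance it calls unknown (planned LEP) while leaving age out of both allocation and analysis, without giving a reason.

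If age predicts 24-month KOOS-4 beyond what baseline KOOS-4 and planned LEP explain, any chance difference in age mix between arms carries into the main estimate. Two things are at stake: a little precision, and the awkwardness of a post-hoc adjustment if the baseline table shows an age imbalance.

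The age provisions already in the plan serve other purposes. Dropping those aged 20 or younger changes the population and leaves imbalance above 20 untouched. The subgroup plot looks for effect modification. Neither adjusts the main estimate.

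**Working it through.** **Inputs from the protocol.** Section 23.2: "Standard nominal 2-sided 5% significance level was adopted"; the chosen size "allows for 15% missing data for a target difference of 9 points (at 90% power"); "given a pooled standard deviation (SD) of 20 points"; "using a correlation between baseline and follow-up score of 0.37". Section 10: 107 per arm.

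**Inputs assumed (not in the protocol).** Share of participants under 20: 10% to 50%. KOOS-4 gap between younger and older participants that remains after the listed model terms: 5 to 10 points.

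**Step 1: the plan's own sample size.** The two-sample non-central t calculation for a difference of 9, SD 20 and 90% power gives 105 per arm, 210 in total. The baseline-adjustment factor is 1 - 0.37² = 0.8631, and 210 × 0.8631 = 181.25. Dividing by 0.85 gives 213.2, hence 214. The stated figure reproduces, and the age point does not alter it.

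**Step 2: standard error.** 214 × 0.85 = 181.9, so about 91 per arm are analysed. Residual variance = 400 × 0.8631 = 345.2. SE = √(345.2 × 2/91) = 2.75 points, ignoring the small contributions of LEP and site.

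**Step 3: chance imbalance.** For a share p under 20 and n per arm, the SD of the between-arm difference is √(2p(1-p)/n), treating age as simply randomised. The 95% half-width is 1.96 times that. The shift in the estimate is the imbalance times the assumed gap.

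| p | 95% imbalance, n = 107 | 95% imbalance, n = 91 | Shift at n = 91, gap 5 | Shift at n = 91, gap 10 |
|---|---|---|---|---|
| 10% | ±8.0 pp | ±8.7 pp | 0.44 | 0.87 |
| 20% | ±10.7 pp | ±11.6 pp | 0.58 | 1.16 |
| 30% | ±12.3 pp | ±13.3 pp | 0.67 | 1.33 |
| 40% | ±13.1 pp | ±14.2 pp | 0.71 | 1.42 |
| 50% | ±13.4 pp | ±14.5 pp | 0.73 | 1.45 |

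With n = 107 the smallest shift is 0.080 × 5 = 0.40. The overall range at the 95% edge is therefore about 0.4 to 1.5 points. The largest value is 1.45/2.75 = 0.53 of a standard error, and the range is about 4-16% of the 9-point target. A one-SD imbalance at n = 91 moves the estimate by 0.22 (0.0445 × 5) to 0.74 (0.0741 × 10) points.

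**Step 4: gain from adjusting.** The share of residual variance explained by an age indicator is p(1-p) × gap²/345.2. The smallest value is 0.09 × 25/345.2 = 0.7% and the largest is 0.25 × 100/345.2 = 7.2%. With 91 per arm, power at 9 points rises from 90.1% to between 90.3% and 92.1%, a gain of about 0.2 to 2 percentage points. The required sample size does not rise.

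**The case against.** The strongest reply is that leaving out one plausible covariate is a legitimate choice. Under randomisation, chance imbalance is ordinary sampling variation that the confidence interval already reflects. That stands: a reader might infer a biased primary comparison or an inflated type I error, and neither follows.

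A reader might also infer that the protocol calls young age a major risk factor for the primary outcome. It does not. The documented risk is re-rupture and graft failure, which are secondary outcomes, and no section says that age predicts KOOS-4. The 5-10 point gap is purely an assumption.

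Nor is age wholly uncontrolled. Planned LEP, partly decided on age, is both minimised on and modelled. Tegner group, which may correlate with age, is minimised on. Section 11.5 sends adolescents to specialist centres, so age should cluster partly by site, which is also in both places. To that extent step 3 overstates the likely imbalance. But LEP is a surgeon's decision resting on several factors, and none of these is an adjustment for age itself.

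Two further inferences fail. The failure comparison is not hit harder because events are few: the shift in a log hazard ratio depends on the imbalance and the age effect, while fewer events widen its standard error. And adjustment does not always improve precision: in a Cox model it changes the target to a conditional hazard ratio and usually raises its standard error. Section 23.3.2 already falls back to an unadjusted model when events are too few.

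Finally, one might say that covariates belong in the SAP. Section 23.3.1 does list the model terms, however, so the protocol itself has fixed a model without age.

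**Conclusion.** The point holds as a modest improvement, not as the repair of an invalid analysis. Age is absent from the minimisation and from the listed primary model terms, and the protocol gives no reason, although it regards age as clinically important.

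Under the assumed 10-50% under 20 and a 5-10 point residual gap, the effect on the main estimate is about 0.4-1.5 points at the edge of the 95% range, at most about half a standard error. The gain from adjusting is about 0.2-2 percentage points of power. If age adds nothing once baseline KOOS-4 and planned LEP are in the model, the gain is nil and the cost is still negligible. The sample size of 214 is unaffected.

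**What to change.** In section 23.3.1, add baseline age as a prespecified fixed effect in the primary KOOS-4 model, preferably as a continuous term. A continuous term avoids relying on an age cut that the protocol has not reconciled: 20-year-olds are removed with the younger group in the 23.3.1 sensitivity analysis but fall in the older group in 23.5.

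The cost is one added term and one degree of freedom of about 180. Age is already collected (section 10.9), so no new data are needed, and prespecifying it now removes any need for a post-hoc adjustment. Adding age to the Cox models for graft failure and re-operation, or to the minimisation, is optional and not needed for this fix.

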15.3.1 Justification for stratification factors

Stratification by pre-injury Tegner score will ensure that the groups will have equal allocations of high (7-10) and low (0-6) pre-injury activity scores, where scores greater than 7 indicate participation in competitive sports.

Stratification by planned lateral extra-articular procedure (yes, no) will ensure that the groups will have equal allocations of an optional additional surgical procedure included at the surgeon's discretion. It is not known if this factor is a confounder.

Stratification of site will ensure that differences in caseload and site level care (pre, post operative) is balanced between treatment groups. This may also help with any differences in costs associated with either group at site level.

15.4 Back-up randomisation/registration procedure

Sites will call the Central CTU Study Team based in Oxford if REDCap is offline or not available. An emergency randomisation list prepared by the study statistician, and held securely by the Central Study Team, will be used.

16 SUB-STUDIES/TRANSLATIONAL STUDIES/MECHANISTIC STUDIES

No sub-studies (related to the study) are currently included.

17 STUDY ASSESSMENTS/PROCEDURES AND DATA COLLECTION

The study flow chart can be found in Appendix 1 of this protocol.

17.1 Overview

Table 1 shows scheduled assessments for the study.

Table 1: Schedule of assessments

Assessments	Screening	Baseline	Day of Surgery	3- & 6-weeks post randomisation	6 months post randomisation	12 months post randomisation	24 months post randomisation
Screening - Identification	*						
Screening - Eligibility	*						
Patient information given	*						
Consent		*					
Eligibility confirmation			*				
Randomisation			*				
Surgeon confidence in the ACL surgery performed (Surgery CRF)			*				
Demographics	*						
Post operative pain (pain NRS) via SMS message, email or post				*			
KOOS (Patient Questionnaire)		*			*	*	*
EuroQol-5D-5L / VAS (Patient questionnaire)		*			*	*	*
EuroQol-5D-5L / VAS Retrospective Baseline - Pre-injury (Patient		*					
questionnaire)							
Emotional functioning (Patient questionnaire)		*			*	*	*
Tegner (Patient questionnaire)					*	*	*
Modified Tegner (Patient questionnaire)		*					
Patient satisfaction (Patient questionnaire)						*	*
Time to return to sport (Patient questionnaire)						*	*
Physio attendance (completed once the pt has been discharged from						*	*
post-op physiotherapy, or at 24 months post-randomisation)							
Resource use /Health economics (Patient questionnaire)					*	*	*
Intervention related complications including re-operation (Patient					*	*	*
questionnaire -> Hospital records check -> Complications CRF)							
+ Intra-operative complications (Surgery CRF)+ Post-operative, pre-discharge complications (InPatient CRF)			*				
Intervention related complications including re-operation (Hospital							*
records check -> Complications CRF)							
Safety data collection			*		*	*	*
Objective evidence of graft/repair failure (defined on clinical assessment, imaging or operative assessment) (Hospital records check) (if required)			*		*	*	*

